9.9 **Research-related Activities:** Research related activities will include both face-to-face and telephone interviews, as well as medical chart extraction. Specific details about each research activity follow below. Data collected from face-to-face and telephone interviews will be collected using REDCap, a secure, web-based application for data collection for research studies.

Baseline Interview:

At the first interview we will ask questions about the participant’s diabetes history, and self-management behaviors related to their diabetes and medication related behaviors. We will also collect standard sociodemographic information. Participants will also complete a cognitive assessment if the interview is completed in-person. The cognitive assessment will not be completed if the baseline interview is completed over the phone.

If the baseline is completed in-person, research coordinators will also perform standardized measurements of blood pressures and pulse using an automated device (validated Omron HEM-907XL or a device with comparable accuracy). Three recordings will be performed at each visit and the mean of the second and third readings will be used to indicate the blood pressure for that visit. Patient positioning, arm selection, cuff size selection and other techniques will follow the procedures for

Regimen Education and Messaging in Diabetes (REMinD)

blood pressure measurement of the National Health Examination and Nutrition Survey. Blood pressure readings will not be performed if the baseline is completed over the phone.

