The 3 month interview will take place over the phone and patients will be asked additional questions about how they take their medicines, their diabetes as well as gather information about receipt of UMS tools, filled prescriptions and text reminders.

The 6 month follow-up interview will take place in-person or over the phone and will gather information about receipt of UMS tools, filled prescriptions, text reminders, self-report of physician medication-related communication at recent encounter as well as complete 3 additional blood pressure readings, and the pill count. The blood pressure reading will be excluded if the interview must be completed over the phone. If the interview is completed over the phone, the same pill count protocol for baseline will be followed for 6 month. For patients consented before May 19, 2020, a brief

Regimen Education and Messaging in Diabetes (REMinD)

script will be read informing patients of the change in the consent in regards to the pill count. The RC will ask the participant to provide verbal consent to allow the study team to take a screen shot/photograph of the patient's pills during a video call in order for the RC to count the pills after the interview. The patient will be notified that no PHI will be captured in the photograph.

At the 6 month interview, in addition to the activities that will take place during the 3 month interview, patients from the intervention arm will also be asked additional, semi-structured questions to explore 1) personal challenges with regimen adherence, 2) perceived value of the EHR and SMS tools, 3) unmet needs and acceptability of other tools and approaches to support medication use.

Clinic Staff Feedback

Among consenting physicians, we will ask physicians to complete a brief survey about their experience using the tools. (See Provider feedback survey)

Medical Record Extraction:

Additional chart data will be abstracted via an additional EDW report including patient medications, chronic conditions, COVID-19 diagnosis an/or results of antibody test, and healthcare utilization (ED, hospitalization, primary care appointments) as well as hypertension, diabetes and cholesterol clinical values. Furthermore, we will extract whether patients received prescription orders in UMS format (with after-visit summaries) and the corresponding. We will also note when (days post visit) the Medication reconciliation sheet was incorporated into the EHR.

Field Notes:

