The project manager will meet monthly with clinic administrators to document any changes that might have occurred and when. This will include relevant change to clinic staffing, workflow, EHR, or any significant event that could potentially alter the delivery and subsequent effectiveness of intervention. The project manager will keep a document of this.

Retention Activities:

In order to maintain high retention of enrolled participants we will mail holiday cards to participants annually. In addition, if we are unable to contact enrolled participants we will mail or email "Trying to Reach You" letters to re-engage participants. Data sources for this study will include in-person and telephone interviews with participants (see attached surveys), and medical record data extraction via the EDW.

For patients that complete COVID-19 Waves 5-9:

★ **Patient Interviews.** Participants will complete up to five telephone interviews in total, with one interview taking place every 4 months. New, supplement-specific data collection related to COVID-19 will be collected via telephone interviews; this survey is equivalent for both Aim 1 and Aim 2 activities, as data collection will be conducted in parallel.

★ **EHR data.** Medical record data will be collected via the Electronic Health Record (EHR) from January 1, 2019 - present. EHR data will confirm comorbidities

Regimen Education and Messaging in Diabetes (REMinD)

and medications. We will also extract clinical outcomes (HbA1c, diastolic and systolic blood pressure, cholesterol (LDL, HDL, total, triglycerides), GFR, COVID-19 lab tests and results, COVID-19 diagnosis, COVID-19 vaccine type and dates, and antibody results), preventive services utilization (cancer screening, immunizations), and health services use (clinic visits (including telehealth), medical subspecialty visits, emergency department visits, hospitalizations). Lastly, we will collect patient portal usage.

★ **Pharmacy fill data.** Participants will be asked if they use Walgreens or CVS to fill their prescriptions. During the consent process, participants will be informed that Walgreens and CVS Pharmacy may access, receive, or use their personal information, based on the pharmacies they utilize. *Data Collection:*

All interview measures and timepoints are listed in the table below.

Variable	Instrument(s) or Measure(s)	Source	Timing & Window		
			0	3M	6M
			60 - 120 days	5M - 8M?	
Outcome Measures			In-person or phone	Phone	In-person or phone

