Medication Adherence	ASK-12	Matza, 2009	x	x	x
	24-hour recall		x	x	x
	Pill Count		x		x
Proper medication use	24-hour recall		x	x	x
Medication consolidation	24-hour recall		x	x	x
Treatment knowledge	Identification of drug purpose		x	x	
Clinical outcomes	HbA1c	chart	x		x
	systolic/diastolic blood pressure	in-person	x		x
Patient Covariates					
Medication Regimen Characteristics	Prescription medication, complexity (MRCI)	George, 2004	x		x
	drug class	George, 2004	x		x
Health status	Overall Health (Global)	PROMIS	x		x
	Comorbidities	Goodman, 2013	x		x
	Depression - SF (4 item)	PROMIS	x		

Regimen Education and Messaging in Diabetes (REMinD)

Health Literacy	NVS, Brief health literacy screener	Weiss, 2005; Chew, 2008	x		
Cognitive Status	MMSE	Folstein, 1975	x		
Patient Activation	CHAI	[name], 2017	x		x
Social Support	Tangible Support	Wolshin, 1997	x		
Sociodemographics	Age, sex, race/ethnicity, education, income, language, English proficiency, country of origin, time in US	self-report	x		
Patient Process Outcomes					
Patient/Provider Communication	CAHPS - Providers discuss medication decisions		x	x	x
Perceived Values of EHR and SMS Tools	Open-ended questions				x
Unmet needs and acceptability of tools	Open-ended questions				x
Personal challenges with medication regimen	Open-ended questions				x
System Process Outcomes					
Receipt of UMS Materials	Receipt of MedSheet (yes/no), UMS Sigs (yes/no), MedList (yes/no)	self-report, chart	x	x	x
Receipt of SMS text reminders	Receipt of SMS (yes/no)	self-report		x	x
Intervention impact on clinic practice	Provider Survey				x
Changes throughout intervention within clinic practice	Field notes with administrative staff				
Cost Outcomes					
Initial programming cost of EHR tools			x		
Programming maintenance costs for EHR					x
Running UMS technologies	Printer ink, paper, staff time		x		
SMS monthly costs			x		

9.10 COVID-19 Survey. We are proposing an optional sub-study to be conducted from a pool of existing studies conducted by [name] (LitCog (STU00026255), REMinD (STU00203777), COPD Multimorbidity (STU00201640), UMS Portal (STU00201639), and TAKE IT (STU00204465). Participants will be invited to participate

Regimen Education and Messaging in Diabetes (REMinD)

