interventions will be estimated relative to usual care from the perspective of NMHC, NM Regional Medical Group, and MSMC practices implementing these processes and tools. First, we will document the initial costs associated with programming the EHR tools at a new site, following the code and standard operating manual guidance from Aim 3. The primary costs of running these UMS technologies in the EHR arm involves the limited expenses around printing the EHR tools (printer ink, paper, staff time) as a result of generating new Rx information with after-visit summaries. SMS monthly costs will be easily documented from EZText invoices as well as usage. However, we will include estimates for programming maintenance for Epic EHR, and will test the sensitivity of results to changes in the maintenance requirements in terms of programmer hours, calculated per site. We also will separately track development costs for software and other programming requirements based on programmer hours. Staff/programmer costs will be measured using tracked time spent on the intervention and wage estimates. We will test the sensitivity of operational costs to different assumptions about the potential use of variable staff using different salaries but assuming the same proficiency in terms of time required. Further, we will assess the sensitivity of estimates to different proficiency levels that could arise from learning by doing.

Exploratory Analyses. We will repeat all GLMM analyses described for Aim 1 to explore whether differences in interventions vary by relevant covariates representing patient and regimen characteristics known to impact outcomes, specifically adherence. Interaction terms will be included in models accordingly. As adherence has its many measurement challenges, experts recommend triangulating with multiple measures. We will compare results across each adherence measure (ASK-12, 24-hour recall, pill count) and create a general estimate of adherence via single factor score using maximum likelihood estimation. Exploratory analyses will examine HbA1c and blood pressure from baseline to 6 months, although power may be limited. Additionally, we will construct marginal models for all primary and secondary outcomes using generalized estimating equations (GEE) in a process similar to those described for the GLMMs. The purpose is to obtain population-averaged estimates of any differences in outcomes across arms vs. estimates at participant level.

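### Study blood pressure is skipped at every phone interview, and the plan makes no use for this outcome of the hypertension values it already extracts from the record

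*Combined protocol and SAP*

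**What the plan says.** All references are to the combined protocol and SAP.

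- **Measurement (9.9, Baseline Interview).** At an in-person baseline the coordinator takes three automated readings, and the mean of the second and third is used. For phone baselines, "Blood pressure readings will not be performed if the baseline is completed over the phone".
- **6 months (9.9, Follow up Interviews).** "The 6 month follow-up interview will take place in-person or over the phone", and "The blood pressure reading will be excluded if the interview must be completed over the phone".
- **Source (9.9, measures table).** The row "systolic/diastolic blood pressure" is marked at 0 and 6 months with an in-person source. The HbA1c row just above it has the chart as its source.
- **Record data (9.9, Medical Record Extraction).** The EDW report for the main trial covers utilisation "as well as hypertension, diabetes and cholesterol clinical values". No measurement window and no analysis use are given.
- **COVID-19 Waves 5-9 (9.9).** For these participants only, the record extract names the readings expressly: "We will also extract clinical outcomes (HbA1c, diastolic and systolic blood pressure, cholesterol".
- **Analysis (11.1, Exploratory Analyses).** "Exploratory analyses will examine HbA1c and blood pressure from baseline to 6 months, although power may be limited". No source of blood pressure values is named here, and there is no rule for missing readings.

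**The concern.** A comparison of blood pressure from baseline to 6 months needs readings at those times. As written, a phone interview removes the reading and nothing takes its place. The other outcomes in the same table are better protected: the pill count has a phone and video procedure, and HbA1c comes from the chart.

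Phone mode is not a rare exception either. The measures table allows it at both time points, and section 28.1 says in-person interviews could not be held under the COVID-19 restrictions.

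Two things are at stake. One is precision, for an outcome whose power the plan already calls possibly limited. The other is coverage: the loss follows calendar time, so patients with device readings would mainly be those seen outside the restriction period. Meanwhile the study collects record data that may hold blood pressure for the missing patients and does not say what it will do with them.

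**Working it through.** **Inputs from the documents.** Target 900 patients and 80% retention (11.1). Recruitment 36 months, follow-up 6 months, nine further months for analysis, analysis complete at the end of July 2022 (7.0). The documents date neither the start of recruitment nor the switch to phone. Two dates in the text can serve as cut dates: 13 March 2020 (start of the outbreak period, COVID-19 survey text in 11.5) and 19 May 2020 (consent change for the phone pill count, 9.9).

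**Denominator.** 900 × 0.80 = 720, or 240 per arm. This reproduces the plan's figure.

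**Calendar.** Section 7.0 does not say when the nine months begin, so there are two readings.
- *Reading A: they follow the last 6-month visit.* 6-month visits run from 1 November 2018 to 31 October 2021, and recruitment from May 2018 to April 2021.
- *Reading B: they run from the end of recruitment.* 6-month visits run from 1 May 2019 to 30 April 2022.

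**Share without a 6-month device value.** Formula: days of the 6-month-visit period that are phone-only ÷ 1,095 days, assuming even accrual. The end dates for phone-only working are assumptions.

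| Phone-only ends | Reading | Cut 13 March 2020 | Cut 19 May 2020 |
|---|---|---|---|
| 30 Sept 2020 | A or B | 201/1,095 = 18.4% | 134/1,095 = 12.2% |
| 31 March 2021 | A or B | 383/1,095 = 35.0% | 316/1,095 = 28.9% |
| 30 June 2021 | A or B | 474/1,095 = 43.3% | 407/1,095 = 37.2% |
| Never | A | 597/1,095 = 54.5% | 530/1,095 = 48.4% |
| Never | B | 778/1,095 = 71.1% | 711/1,095 = 64.9% |

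If in-person visits never resumed, Reading A loses 348 to 393 of 720 and leaves about 109 to 124 per arm. Reading B loses 468 to 512 and leaves about 69 to 84 per arm.

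**Share without a device pair (Reading A).** A phone visit at either time breaks the pair, so the enrolment dates affected run from six months before the cut to the end of phone-only working.
- Ends 30 September 2020: 383/1,095 = 35.0% (March cut). With the May cut the two affected groups do not overlap: 2 × 134 = 268, and 268/1,095 = 24.5%.
- Ends 31 March 2021: 565/1,095 = 51.6% (March) or 498/1,095 = 45.5% (May).
- Ends June 2021 or never: 54.5% or 48.4%. Every later enrolee already has a phone baseline or a phone 6-month visit.

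**Precision.** For two means, the detectable difference scales as 1/√(1 − share missing). At two-sided 5%, 80% power and 240 per arm, ignoring clustering, it is (1.960 + 0.842) × √(2/240) = 0.256 SD.
- 24.5% missing: × 1.15, giving 0.29 SD.
- 50% missing: × 1.41, giving 0.36 SD.
- 54.5% missing: × 1.48, giving 0.38 SD.

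**The case against.** **The size is not on the page.** A reader might infer from the timeline that about half of the patients have no 6-month blood pressure. The documents do not support that as a fact. It needs Reading A, even accrual and no return to in-person visits. The current text leans against the last of these: the 6-month visit may still be in person, section 22.2 still pays cash at an in-person 6-month interview, and the reading is dropped only when a phone interview is unavoidable. This stands, and half is one scenario in a wide range.

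**A pair may not be required.** Section 11.1 defines no change score and no complete-case rule. A mixed model on all observed values would keep patients with one reading. This also stands. It moves the loss from the pair to the single time point, but the phone reading is still absent.

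**The plan may intend to use chart values.** The table lists interview measures, and 11.1 names no source. However, the table gives chart as the source for HbA1c and in-person for blood pressure, and no text assigns the hypertension values to this outcome. Nor does the main-trial text say that these values are blood pressure readings. Only the Waves 5-9 extract does, and only 136 patients from this trial had joined that cohort.

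**Chart values are a weak substitute.** A reader might conclude that they should become the main analysis. The documents do not support that. Routine office readings do not follow the three-reading protocol, and they may be sparsest where care moved to telehealth, which is when the gap arises. This limits the remedy to a supplementary role.

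**The consequence is small.** Blood pressure appears in no hypothesis and is neither the primary nor a secondary outcome. A calendar-driven gap should affect all arms, and nothing shows that loss differs between them.

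**Conclusion.** The gap is real. Followed as written, the plan yields no device reading at any phone interview, so a patient with a phone visit at baseline or 6 months has an incomplete device record for the 11.1 analysis. The extracted hypertension values have no stated role in filling it.

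The size is an assumption with a range. About 12% to 71% of 6-month device values are missing, depending on when the nine analysis months start and whether in-person visits resumed. About 24% to 54% of patients lack a device pair if the nine months follow the last visit. Both ranges assume even accrual and a switch to phone between March and May 2020.

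The effect is on the precision and coverage of one exploratory outcome. The primary adherence analysis is untouched. This is a worthwhile, inexpensive improvement and not a flaw in the trial's main inference.

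**What to change.** 1. Confirm that the EDW hypertension values include dated systolic and diastolic readings at both sites.
2. Keep the standardised device-to-device comparison for patients with in-person readings. State in 11.1 whether it uses change scores or a model for all observed values.
3. If step 1 is confirmed, add chart blood pressure to the measures table as a second source, and a prespecified supplementary analysis to 11.1. Use EDW values at both times, with fixed windows around baseline and 6 months. For example: the last value within 90 days before baseline, and the value nearest 6 months within the interview window. That window is printed as five to eight months with a question mark, so it must be settled first.
4. Do not mix sources within a patient.
5. Report by arm the number of patients with device and with chart readings at each time, and the number with a pair from each source.

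The cost is SAP wording and analyst time on an extract already planned, with no new visits. The downside is that office readings are less standardised and may be sparse where care moved to telehealth, so the gain in coverage should be reported and not presumed.

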The IOM 2008 report *Standardizing Medication Labels* recognized the need to set standards for prescribing and dispensing practices to promote safe and accurate medication use.⁷⁰ Members of our research team ([name], [name]) presented the UMS concept in this report. As nearly 90% of prescriptions are taken 4 times a day or less, the UMS specifically proposed to establish 4 standard time intervals (morning, noon, evening, bedtime) for the prescribing and dispensing of medicine. This would remove current variability in the way prescriptions are written by physicians and transcribed by pharmacists.⁶⁷⁻⁶⁹ All prescriptions would instruct patients to take their medicine at one or more of these specified times; this would be described in a single, standardized fashion (**Figure 1**). UMS instructions also use health literacy best practices, like simplified text, numeric characters instead of words to detail dose (1 instead of 'one'), and carriage returns (placing each dose on a separate line) to clearly identify every time a medicine is to be taken.⁴

Figure 1. The Universal Medication Schedule (UMS)

Take	1 pill in the morning	
Take	1 pill in the morning 1 pill in the evening	⌚ Morning: 6-8 am
Take	1 pill in the morning 1 pill at noon 1 pill in the evening	⌚ Noon: 11-1 pm
Take	1 pill in the morning 1 pill at noon 1 pill in the evening 1 pill at bedtime	⌚ Evening: 4-6 pm ⌚ Bedtime: 9-11 pm

Regimen Education and Messaging in Diabetes (REMinD)

There is strong evidence supporting the UMS.^{4,70-77} Among a multi-site sample of 500 primary care patients, [name] et al. found those receiving UMS instructions versus a current standard were 33% more likely to accurately interpret Rx instructions.⁷² Lower literate adults were more likely to correctly comprehend the UMS instructions. These findings were replicated among 94 patients in Cork, Ireland, and also among 203 LEP patients in Chicago and San Francisco.^{73,74,78} Earlier studies also found the use of more explicit time intervals, such as those used in the UMS approach, improved patient understanding and reduced medication errors.^{72,79}

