3.0 Inclusion and Exclusion Criteria

3.1 Patient Inclusion Criteria:

1) 21 or older, 2) Type 2 diabetes mellitus diagnosis, 3) Seek care at family medicine or general internal medicine practices in the Chicago-land area (Northwestern) or New York City (Mt. Sinai), 4) English or Spanish speaking, 5) Take 5 or more prescription drugs for chronic conditions, 6) Adequate visual acuity and hearing, 7) Adequate cognitive capabilities to consent to participate, 8) primarily responsible for administering their own medication, 9) own a cell phone and are comfortable receiving text messages, 10) most recent hbA1c value $\geq 7.5\%$.

3.2 Provider Inclusion Criteria:

1) Resident, Attending Physician or Mid-level provider (NP, PA, pharmacist) working in General Internal Medicine, primary care, or family practice clinics within NMHC, Northwestern Medical Group, or NM Regional Medical Group (RMG) during study dates.

3.3 Adults unable to consent, individuals under the age of 21, and prisoners will be excluded from this research.

3.4 COVID-19 Survey Eligibility:

Wave 1: We will include any participant who has consented to participate in the main study and who has indicated that they were willing to be contacted for future studies run by [name] on the consent form.

Waves 2 – 4: We will include any participant who has consented to participate in the main study, who has indicated that they were willing to be contacted for future studies by [name] on the consent form, and who completed at least Wave 1 of the COVID-19 survey.

Waves 5 – 9: We will include any participant who has consented to participate in the main REMinD study, who has indicated that they were willing to be contacted for future studies by [name] on the REMinD consent form, and who completed at least Wave 1 of the COVID-19 survey.

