based on the distribution of the outcome variable. The GLMMs will include random provider effects and fixed binary variables for SMS text reminder and EHR to denote the intervention groups and the usual care group (H1-4). We will include a fixed indicator variable for clinic in the GLMMs and any potential confounding covariates as noted above. Analyses will be performed using PROC GLMMIX in SAS (v.9.3) and lme4 package in R. Since understanding and adherence will be assessed for each medication, 2-level GLMM will be used with medications nested in participants. We will first test for differences in the outcomes between the EHR group and usual care (H1-3), followed by comparisons between EHR+SMS vs. usual care, and EHR vs. EHR+SMS to determine additional benefits of SMS texting (H4) by constructing contrasts.

Aim 2

We will include both literacy-by-arm and language-by-arm fixed interaction terms in the above GLMMs for all outcomes. We will use the corresponding model type III tests for fixed effects to determine significance of terms, and construct appropriate contrasts for pairwise comparisons for each literacy level and each language.

Aim 3

We will determine the extent to which the interventions were implemented as planned (a process evaluation) across each site and for all three study arms, in order to optimize the intervention for future dissemination opportunities.

Mixed methods will be employed using a convergent parallel design to obtain data on intervention implementation.

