Quantitative and qualitative findings will be merged to answer 1) whether either intervention was implemented as planned, 2) from a user-perspective, do interventions require modification and how. In this approach, both analyses are conducted separately and merged for side-by-side data comparisons. For quantitative data (patient report, EHR data), frequencies will be generated to determine outcomes related to receipt of materials, perceived helpfulness of materials, CAHPS and PACIC. For CAHPS and PACIC data, similar GLMM models as described in Aim 1 analyses will be performed, with intervention arm as the primary independent variable. For qualitative data, we will review and explore the transcribed patient interviews and clinic staff discussions using content and ethnographic analysis. Predetermined categories will organize feedback from all users: patient, provider, clinic/health system. Within each of these broad categories we will use a predetermined coding approach to quantify the frequency of two subcategories: facilitating factors, and impeding factors (see Figure 8). An additional layer within impeding factors would be whether factors are modifiable or not, and under facilitating factors, if they are replicable. Field notes and quantitative findings will be integrated in this model. Transcribed interviews and field notes will be examined by the study team independently to see if modifications to the categories are needed.

Aim 4:

We will directly measure and assess the provider perspective costs of developing and running UMS interventions, alone and in combination. Incremental cost of

Regimen Education and Messaging in Diabetes (REMinD)

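### Receipt of UMS sigs and MedSheets is a yes/no per tool with no unit, denominator or threshold, so it cannot show how fully the tools were delivered, which is what Aim 3 asks

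*Combined protocol and SAP*

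**What the plan says.** The measures table in section 9.9 lists, under System Process Outcomes, "Receipt of MedSheet (yes/no), UMS Sigs (yes/no), MedList (yes/no". The sources are self-report and chart, and the item is marked at baseline, 3 months and 6 months.

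For the chart source, Medical Record Extraction in section 9.9 says "we will extract whether patients received prescription orders in UMS format (with after-visit summaries) and the corresponding". The sentence breaks off there, so a further extracted item may have been lost from the text.

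For the analysis, the Aim 3 part of section 11.1 says that "frequencies will be generated to determine outcomes related to receipt of materials". Models are named there only for the CAHPS and PACIC data.

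The tools themselves work at a finer level. Section 2.2 sets out the UMS prescription by prescription: "All prescriptions would instruct patients to take their medicine at one or more of these specified times". Section 9.6 describes the MedSheet as a one-page sheet whose content starts with the drug name and which draws in that drug's UMS sig. Section 3.1 requires that patients "Take 5 or more prescription drugs for chronic conditions". In Aim 1, the corresponding outcomes are handled by drug: "Since understanding and adherence will be assessed for each medication".

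**The concern.** Aim 3 is a process evaluation of how far the interventions were carried out as intended. That is a question of degree. A patient on five or more drugs can have UMS wording on all, some or none of the prescriptions that were due it, and a single yes/no per tool cannot separate these states.

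Partial coverage matters particularly in this trial. Section 2.3 reports that in the team's earlier work patients went on receiving mixed label instructions and needed to see the UMS applied across the whole regimen. Partial delivery is therefore a failure that Aim 3 should be able to detect. If adherence does not differ between arms, readers will want to know whether the UMS did not help or did not reach the prescriptions. A frequency of undefined yes answers will not tell them.

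**Working it through.** The plan states no receipt rate, fidelity target or threshold, so there is no figure of its own to reproduce. The check applies the measure to example records and then sizes the gap under stated assumptions.

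**Example records, one tool, one time point**

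| UMS orders / eligible orders | Share delivered | Scored if any order counts | Scored if all orders must count |
|---|---|---|---|
| 5 of 5 | 100% | yes | yes |
| 4 of 5 | 80% | yes | no |
| 1 of 5 | 20% | yes | no |
| 0 of 5 | 0% | no | no |
| no eligible order | undefined | no | not defined |

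Under the any-order rule, 1 of 5 and 5 of 5 look alike. Under the all-orders rule, 4 of 5 and 0 of 5 look alike. In the last row there was nothing to deliver, yet a plain yes/no item would naturally record a no.

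**Inputs for the size**
- Number of eligible orders per patient, n: not given. Section 3.1 sets at least five drugs *taken*. Section 29.2, in its justification for a consent waiver, ties patient eligibility to a prescription for a new or changed medicine. Eligible orders over six months may therefore be fewer than five, so n = 1, 2 and 5 are shown.
- True per-order delivery, p: not given; 30% assumed for illustration.
- Within-patient correlation, ρ: not given; 0 (independent) and 0.3 assumed.

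**Formulas**
- Independent orders: any = 1 − (1 − p)^n; all = p^n.
- Correlated orders (beta-binomial): a = p(1 − ρ)/ρ and b = (1 − p)(1 − ρ)/ρ. Then P(none) is the product over i = 0 to n − 1 of (b + i)/(a + b + i), any = 1 − P(none), and P(all) uses a in place of b in the numerator.

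**Numbers for p = 0.30.** With ρ = 0.3, a = 0.700, b = 1.633 and a + b = 2.333.
- n = 1: any = all = 30%.
- n = 2, independent: any = 1 − 0.7² = 51%; all = 0.3² = 9%.
- n = 2, ρ = 0.3: P(none) = 0.700 × 0.790 = 0.553, so any = 45%; all = 0.300 × 0.510 = 15%.
- n = 5, independent: any = 1 − 0.7⁵ = 83%; all = 0.3⁵ = 0.2%.
- n = 5, ρ = 0.3: P(none) = 0.700 × 0.790 × 0.838 × 0.869 × 0.889 = 0.358, so any = 64%; all = 0.300 × 0.510 × 0.623 × 0.694 × 0.742 = 5%.

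The opposite error also appears when delivery is good. At p = 80% and n = 5, the all-orders rule gives 0.8⁵ = 33% if independent and 52% at ρ = 0.3.

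**Patients with no eligible order.** If a share q of patients has none and they are scored no, the frequency of yes is multiplied by (1 − q). Even perfect delivery would then be reported as 1 − q.

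**The case against.** A reader might infer that one UMS order counts as full receipt and that Aim 3 will therefore overstate delivery. The documents do not support that. No section states an any-order rule, and an all-orders rule would give the opposite error, so the text does not fix the direction. Nor is receipt scored once per patient: it is marked at three time points from two sources. The chart-extraction sentence is cut short, and the interview forms, which might define the item, are not in the documents. The heading for sigs in section 9.6 has no description beneath it, so the unit of a sig rests on section 2.2.

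The larger percentages also need caution. Five is the minimum number of drugs taken, not of eligible orders, and with one eligible order the gap disappears. Section 9.2.1 says that the functions are switched on or off by physician, so orders within a patient may well cluster. As the correlation approaches 1, the any-order rate falls to the true rate. The same switch is meant to keep usual-care physicians from having access, so apparent contamination in that arm would be speculation.

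The share of patients reached is a legitimate fidelity measure. Aim 3 also draws on interviews, staff discussions and field notes, and no planned analysis links receipt to adherence.

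All of this stands, and it limits the point to the one made here. It does not remove the point. Under either rule a yes/no discards the degree of delivery, and neither the table nor the analysis text supplies a count or denominator. Qualitative material cannot stand in for a delivery proportion.

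**Conclusion.** The point holds as a weakness of the Aim 3 receipt measure. For sigs and MedSheets, a yes/no per tool with no unit, denominator or threshold cannot answer a question about degree. Its error can run either way, depending on a rule the plan does not state.

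The size is conditional. At an assumed true delivery of 30%, the any-order reading is too high by 0 points with one eligible order, 15–21 points with two and 34–53 points with five. The lower end of each range assumes a within-patient correlation of 0.3 and the upper end independence. The delivery rate, the correlation and the number of eligible orders are all assumptions.

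The yes/no format is suitable for the MedList, which section 2.4 describes as covering the whole regimen. The primary outcome, its test and the sample size are not affected.

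**What to change.** In the measures table and under Medical Record Extraction (both section 9.9), define chart-based receipt of sigs and MedSheets per order:
- **Denominator:** eligible orders, meaning new or changed chronic-medication prescriptions written by study providers from the baseline visit to the 6-month interview. State this trigger explicitly, since the plan mentions it only in section 29.2.
- **Numerators:** eligible orders that carried a UMS sig and, separately, eligible orders with a MedSheet.

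In the Aim 3 text of section 11.1, report both proportions by arm and site, allowing for clustering by patient and provider. Report separately the share of patients with no eligible order, so that lack of opportunity is not counted as failed delivery. Keep the patient-level yes/no as a secondary measure of reach, with its any-order or all-orders rule stated, and as the measure for the MedList.

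The cost is one order-level field in the EDW extract already planned and a short edit to the Aim 3 text. No extra visits or patients are needed. The drawback is that reported fidelity may look lower than a patient-level figure.
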